5.8. General Study Procedures

Specific study procedures will take place at screening and enrollment, and then quarterly for both the standard-of-care arm as well as the intervention arm for up to 12 months. At screening, eligibility information will be collected. Subjects who meet the eligibility criteria will then be enrolled in the study.

Once written consent is obtained, a member of the study team will collect demographic and health questions, related to age, birthdate, income, employment history, prior HIV testing, medical conditions, and current symptoms. They will also obtain each participant's phone number, address, and relevant contact information. After obtaining the baseline demographic and clinical data, they will determine the study group randomization of the participant.

A Research Nurse will then meet the participant in the same clinical exam room, and administer a brief clinical questionnaire. The nurse will coordinate the necessary blood draws for the participant, so each participant will only have one blood draw for each clinical visit. As part of PrEP initiation, several standard of care laboratory tests would have been completed prior to trial entry including HIV-1 testing, serum creatinine, Hepatitis B surface antigen, urine pregnancy test. For this study, additional information will be collected on medical history, physical exam findings, and STI syndromic assessment and additional testing will be done as part of standard of care PrEP follow-up.

PrEP delivery will be according to the 2016 Kenya PrEP guidelines, including measurement of renal function (estimated creatinine clearance >60 mL/min to start PrEP and periodic monitoring over time, aligned to the visit schedule of the study), standard clinical assessment to avoid continuing PrEP during acute HIV-1 infection, and adherence counseling. Subjects will then be randomized at enrollment (Month 0 but the 3—month visit on PrEP) in a 1:1 fashion, as described above. Participants in either arm will be provided 3 months of PrEP medication, corresponding to enough to last until the next clinic-based visit. Participants in both arms will be counseled on PrEP discontinuation according to Kenya national guidelines.

At each study visit, we will offer counseling for participants for HIV-1 testing (pre- and post-testing), HIV-1 infection risk reduction best practices, condom promotion and provision, adherence to PrEP medication, as well as other HIV-1 prevention strategies.

Participant contact tracing for retention at all study visits will be done, particularly to establish PrEP continuation and HIV-1 status.

5.9. Standard-of-Care Arm Follow up Procedures

Participants in the standard-of-care arm will be directed to the regular clinical waiting area to be seen and evaluated by the study team every 3 months until the study end (month #12). The study team will prescribe PrEP and additional medications as appropriate, and provide adherence

counseling as appropriate. The standard-of-care includes rapid testing for HIV-1 before dispensing PrEP. If any participants have become HIV-infected, then confirmatory testing will be performed and participants will receive standard HIV care, including initiation of antiretroviral therapy. Urine and hair samples will be collected and stored at the baseline visit and at months 3, 6, 9 and 12 for all standard-of-care arm participants but not tested (until study end).

5.10. Intervention Arm Follow up Procedures

Participants in the intervention arm will receive the same treatment and evaluations as participants in the standard-of-care arm (**Table 1**). In addition, participants will have baseline and quarterly testing for tenofovir by the POC urine assay test. The results of the test will be provided to the participant by the healthcare research provider and will be used to inform enhanced adherence counseling as above. An image of the point-of-care urine adherence assay is shown in **Figure 6**. The laboratory staff at the Thika site will interpret the test (to deliver the information to the research healthcare provider) and then take a picture of each urine test after development and upload to our centralized database.

5.11. Data Collected and Testing during Clinical Visits

We will use structured interviews on HIV-1 testing practices and self-reported PrEP adherence (e.g., frequency, ability, self-rating, missed doses). **Table 1** provides a summary of clinical visits and testing in both study arms. There will be a window of 20 days around study visits to allow for late visits due to life circumstances.

Table 1. Timeline of Visits and Laboratory Tes	sting				
	Enrollment	Month 3	Month 6	Month 9 Mont	12
Screening and Enrollment					
Review eligibility criteria	X				
Obtain informed consent	X				
Randomization	X				
Collect sociodemographic information	X				
Research Assistant tasks					
Collect and update contact information	X	X	X	X 2	
Conduct baseline questionnaire	X				
Conduct quarterly questionnaires		X	X	X 2	
Conduct exit study questionnaire]	
Perform PrEP pill counts	X	X	X	X 3	
Point-of-care and Laboratory Testing		·	·		
Hemoglobin (for research study)	X	X	X	X 2	
POC urine tenofovir assay with feedback (Intervention Arm)	X	x	x	X 2	

Urine collected and stored (Standard of Care arm)	X	X	X	X	X
Specimen Collection and Storage					
Stored plasma (10 ml)	X	X	X	X	X
Dried blood spot for TFV-DP	X	X	X	X	X
Hair sample for TFV	X	X	X	X	X

*For the standard of care when providing PrEP, all paticipants in the study will receive a medical history and interval updates, physical examination, rapid HIV-1 testing, PrEP or other drug side effect screen, pill counts for PrEP drugs, PrEP dispensing for a 3-month supply, and standard adherence and risk reduction counseling at every visit. Per the standard of care when providing PrEP, creatinine is checked every 6 months, urinalysis every 6 months, and a urine pregnancy test for women is performed as indicated by clinical care. All research providers at the Thika Clinic are trained clinicians in PrEP provision so they will be performing both the research procedures and the standard-of-care clinical procedures for PrEP.

For date collection, we will use electronic data capture (REDCap Cloud), which is currently in use at the Thika site.

5.12. Participant Retention and Withdrawal

The Thika site will develop retention methods tailored to and most efficient for the local study setting. Retention activities may include explanation of the study visit schedule and procedural requirements during the informed consent process and re-emphasis at each study visit, collection and updating of locator information, and use of appropriate and timely visit reminder mechanisms (including phone calls and text messages). Visits can be missed, but, to provide complete information at the end of the study, efforts will be made to have a final follow-up visit for each participant. This study does not allow for home visits.

Participants may voluntarily withdraw from the study for any reason, at any time. If the participant decides to leave the study before her last scheduled study visit, the participant will be requested to have a final study visit with the procedures listed in Table 1. The site Investigator also may withdraw participants from the study in order to protect their safety and/or if they are unwilling or unable to comply with required study procedures. Participants may also be withdrawn if the study is stopped or canceled. Reasons for withdrawal will be recorded.

5.13. PrEP Discontinuation and Seroconversion

PrEP Discontinuation. PrEP continuation will be according to Kenya PrEP guidelines. Use of PrEP may be interrupted by the site Investigator due to safety concerns for the participant or if the participant is unable or unwilling to comply with study procedures. All treatment interruptions will be documented.

Seroconversion will be determined by local HIV-1 testing guidelines. For an initially HIV-1 uninfected participant who seroconverts, she will be exited from the study and referred to HIV primary care for confirmation of the positive result and initiation of HIV care.

Protocol Version 6.0 November 11, 2021 Page 35 of 93

957958

959

960

961

962

963

6. STUDY OUTCOMES AND ANALYSES

6.1. Primary Outcomes

The three primary outcomes for this study will be 1) acceptability of POC urine tenofovir testing among women receiving PrEP in Kenya; 2) feasibility to provide feedback on the POC urine tenofovir assay to participants for healthcare providers, and 3) long-term metrics of adherence as assessed via hair concentrations of TFV and FTC assessed at the 12-month study visit after enrollment.

964965966

967968

969

970

971

972973

974

975

976

977

978

979

980

981

982

983

984

985

986

6.2. Data Collection for Primary Outcomes:

Acceptability for participants taking PrEP: We will conduct a mixed-methods assessment of the intervention arm participants' (all women on PrEP) experiences with real-time monitoring and feedback at the end of the study. A quantitative survey and a qualitative interview guide for indepth interviews of participants will draw from the Information-Motivation-Behavioral skills (IMB) model. 180-187 Quantitative data collection will occur via standardized interviewer-administered questionnaires. Items to be assessed include the following: 1) Feelings about receiving their PrEP adherence results in real time; 2) Likelihood of participating in other studies using a similar design; 3) Likelihood of wanting to receive results of urine testing outside of a study while they are on PrEP; 4) Concern about the privacy and security of the data regarding their urine results; 5) Grading of the potential impact of knowing their urine TFV results on subsequent medication adherence; 6) Advantages and disadvantages of being told about their adherence in real time; 7) Likelihood of taking PrEP just before later study visits because they knew the urine test was being conducted; 8) Preferences regarding a yes/no assay versus an assay that provides information on "high", "moderate" or "low" adherence. A 5-point Likert item format will be used to assess graded items (such as the likelihood of wanting continued urine testing in the context of PrEP; feelings about the urine testing, ranging from negative to positive; concerns about privacy, ranging from low to high; the potential impact of real-time feedback on subsequent adherence, ranging from low to high). Other items (advantages and disadvantages of being told about adherence results) will provide pre-specified options with one "other" option for open-ended text fields.

987 988

989

990

991

992

993

994

995

996

Qualitative data collection for the acceptability outcome will include serial in-depth interviews using pre-piloted semi-structured guides (n=20 women from the intervention arm) and focus group discussions (n=4 groups with 5-10 women), conducted by experienced social scientists acting in the roles of facilitator and note taker under [name] supervision. The semi-structured interview guide will elicit feelings about the adherence metric and counseling messages, concerns regarding privacy, advantages and disadvantages of receiving such results, the likely impact of this monitoring test on sustained adherence to PrEP or just short-term adherence. Although the guide will provide a framework for discussion participants will be encouraged to share their own thoughts regarding the feedback from the POC tenofovir assay. The in-depth interview will be

conducted at the end of the study (month 12). The focus group discussions will also be conducted at study exit. Interviews will be conducted using the participants' preferred language and by consensus in the focus group discussions. The sampling for the qualitative interviews to include a range of possible perspectives (stratified-purposive sampling), to allow for stratification by study arm and other relevant factors that may emerge during the interviews. For instance, women will be purposefully sampled based on age group (≤ or > 25 years) given unique adherence barriers among young women. ^{63,188,189}

100310041005

1006

1007

1008

1009

1010

1011

1012

1013

1014

10151016

1017

1018

1019

1020

997

998

999

1000

1001

1002

Feasibility for research healthcare providers: Under the supervision of [name], who has led qualitative work in Thika for the past decade. 190-196 we will assess the feasibility of the intervention by interviewing research healthcare providers, who will be administering this test at the clinical point of care in the future. The urine test takes 2 minutes and should be feasible in the context of busy clinic visits. We will examine provider perceptions of the assay using in-depth interviews. These key informant interviews (up to 8) will be performed at the end of this study with the healthcare providers (nurses, doctors, counselors) who delivered the counseling messages to intervention arm participants after receiving the results of the POC urine TFV assay from the trained Thika laboratory staff. We aim to understand acceptance, barriers, facilitators, and confidence regarding PrEP adherence testing using this POC assay in the context of PrEP. The semi-structured interview guide will draw from the Unified Theory of Acceptance and Use of Technology (UTAUT) model.{Ventkatesh, #603} This model incorporates factors that influence technology acceptance (in this case, of the POC immunoassay): perceived usefulness (performance expectancy), complexity to use (effort expectancy), stigma/social harm (social influence), and benefits (facilitating PrEP adherence among patients). These interviews will also elicit barriers and facilitators to delivering the TFV assay-informed counseling messages. Suggestions on how to optimize delivery of PrEP adherence testing will be documented.

102110221023

1024

1025

1026

1027

Storage and Retention of qualitative data sets:

The qualitative discussions for both the Acceptability and Feasibility data collection procedures will be recorded, transcribed, and translated into English by the study team. All source documents including audio-recordings and notes for qualitative data will be stored in secure and lockable cabinets in accordance with the DAIDS Storage and Retention of Clinical Research Records Policy.

102810291030

1031

1032

1033

1034

1035

1036

Impact on hair concentrations (long-term adherence).

Small hair samples (~50-100 strands) will be collected at study visits using previously described methods.²³ TFV concentrations in hair samples will serve as the metric for cumulative, long-term adherence to PrEP. TFV and FTC are measured in hair samples at the Hair Analytical Laboratory at the University of California San Francisco (UCSF) using validated methods. The Hair Analytical Laboratory (HAL), and its predecessor (the UCSF Drug Studies Unit), have vast expertise (since 1977) in LC-MS/MS-based methods to analyze drugs in a variety of matrices, including

antiretrovirals (ARVs) in hair. 9,10,30 The trial will assess whether TFV levels in hair increase over time with delivery of the feedback results and the opportunity to perform enhanced adherence counseling. Moreover, the combination of short-term adherence metrics (urine tenofovir assay) and long-term adherence metrics (hair TFV assay) in this study will enable us to determine if there are white-coat patterns of adherence. 35,39,41 For example, positive urine TFV assays but low concentrations of TFV in hair (in intervention arm participants or in both arms, as assessed at the end of the study) are suggestive of white-coat adherence patterns. PrEP refills will be measured through data from the clinic's electronic pharmacy system.

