The UCSF Hair Analytical Laboratory (directed by [name]) has now developed a collaboration with Alere™ (recently bought by Abbott Rapid Diagnostics), a company with vast expertise in point-of-care (POC) diagnostics, to develop one of the first immunoassays that detects TFV in urine. The test is sensitive, specific, precise, and quantitates TFV levels in urine as accurately as LC-MS/MS,¹.².⁴ or enzyme-linked immunoassay⁵ allowing for low-cost POC adherence monitoring. The first iteration of the lateral flow immunoassay (LFA) has been developed⁴ and allows for real-time testing, giving the provider qualitative yes/no information on recent adherence to PrEP. This novel POC adherence assay has the potential to address key knowledge gaps in PrEP implementation to both interpret and improve adherence.

Aim:

To perform a pilot randomized controlled trial (RCT) in Kenya to assess the acceptability of the urine POC TFV assay to participants, the feasibility of administering the test for providers, and the impact of real-time adherence monitoring/feedback via the POC test on increasing PrEP adherence over time (as established by a long-term metric of adherence using hair levels).

Hypothesis: Providing real-time monitoring/feedback via the POC assay will be acceptable, feasible, and improve adherence over time among adherence-challenged women on PrEP in Kenya.

Given known PrEP adherence challenges among women not in serodiscordant couples and the likely need for daily drug-taking among women for efficacy,⁵⁰ we will conduct a pilot randomized controlled trial by randomizing women not in serodiscordant couples on PrEP in Kenya to standard of care adherence counseling (n=60) vs real-time adherence feedback and enhanced adherence counseling using information from the POC urine assay (n=60). Using mixed-methods, we will assess the acceptability of the test to participants and the feasibility of administering the test for providers via triangulating data from

Approach:

structured surveys and qualitative interviews. The effect of the feedback on long-

term adherence over time measured via tenofovir (TFV) levels in hair samples will

At study end, we will have conducted a field test of a novel lateral flow assay to detect TFV in

urine as the first POC low-cost objective adherence metric available for participants on PrEP. The

assay will launch a novel modality for adherence intervention. Moreover, study findings will inform

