Appendix V: Qualitative Guide for In-Depth Interviews (IDIs) for Providers

Introduction

2739 *[~5 minutes]*

27402741

2736

27372738

Interviewer will introduce herself to the provider.

27422743

2744

2745

2746

2747

2748

Thank you for coming today to participate in this interview. We have asked you to participate in this discussion because you provide care and treatment services for individuals who are at higher risk for acquiring HIV. We're conducting this interview to get your input on a point-of-care test that we used in the PUMA study. As you know, this test can measure a person's adherence to pre-exposure prophylaxis (PrEP) by measuring whether tenofovir is found in the person's urine. The goal of this interview is to understand your feelings about this test and to discover potential applications and use cases for this test.

274927502751

2752

2753

2754

2755

2756

2757

2758

2761

We really appreciate you taking the time to talk with us today. The interview should take about 30-60 minutes. We are going to audio record the conversation in order to capture all the details and summarize them later on. For that reason, please do not use your name, other people's names, or organization names to ensure we maintain the confidentiality of the interview. We will also be taking notes during the discussion to use as a reference. After we've transcribed the interview, we will delete the audio recording. Please remember that participation in the interview is completely voluntary, and you may decide to not answer any question as you wish, and you can leave at any time.

27592760

Please feel free to think out loud and answer questions as honestly as possible. And remember that there are no right or wrong answers.

27622763

Are there any questions before we begin?

Do I have your permission to record this discussion? [If provider answers yes, turn on audio recorder.]

2766

2767

2770

2771

2773

2775

Discussion Guide

Probes:

2768 1. To begin, please tell me about your role in the PrEP program.

- a. What do you do on a day-to-day basis?
- b. How do you interact with patients on PrEP?
- 2772 2. How long have you been in this role? (years/months)
 - 3. How do you monitor or assess PrEP adherence at Thika clinic? If at all?
- 4. How easy or difficult is PrEP adherence for your PrEP clients?
 - a. Would you say non-adherence is common?

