- 5. How comfortable are women in reporting adherence challenges with PrEP to you or other providers in the clinic? Please explain.
- 2778 6. Does the clinic provide counsel or support around PrEP adherence- trying to take PrEP every day? Please tell me about that.
 - a. Please give some examples of the support services are provided. (For example, do providers spend time counselling patients on the importance of taking PrEP every day? If so, how often is this done?)
 - b. What do you think about the quality of support provided to PrEP clients to improve their adherence? Is it helpful? Are clients responsive to this support?

II. Present the urine assay strip picture

2780

2781

2782

2783

2784

27852786

2787

2788

2789

2790

2791

279227932794

2795

2796

2797

2798

2799

2800

2801

2802 2803

2804

2805

2806

28072808

[Interviewer to bring out the rapid strip urine picture below and show it to the provider]

Interviewer: This is a new test that was developed that can be used to measure people's adherence to PrEP during their clinic visit. We used this in the PUMA study and half of the clients received counseling based on the results of this test and half of the clients received standard-of care counseling.

You saw that all the client has to do was to provide a urine sample, and the provider then dips this strip into the urine sample (up to the test line indicated) and the strip will tell the provider the results at that moment (within about 5 minutes).

The strip tells the provider whether the client has taken their PrEP drugs (yes/no) in the last 4 days. A colored line at the top of the test when dipped into urine means no (has NOT taken PrEP drugs in the last 3 days) and no colored line means YES (has taken PrEP drugs in the past 3 days).

- If the test shows no colored line, it means that person has taken PrEP in the past 4 days (YES)
- If the test shows a colored line, this means that the person hasn't been able to take their PrEP pills for a while (NO)
- Please note that this is the opposite of other rapid tests that we are familiar with, such as pregnancy tests.

III. Elicit feedback about the test

- General thoughts on clarity of test: Now I'm going to ask you about what you thought about this new test.
- 2811 1. What were you first thoughts about this test?
 - a. What do you like about it?
 - b. What do you dislike about it?

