 - 2. How clear were the results to you? Or was it confusing? What makes these results clear or confusing?

2818

2819

2820

2821

2822

2823

2824

2825

2826

2812

2813

2814

Applications of PrEP Adherence Testing

- 1. Do you think there would be any benefits or negative effects of using this test on your HIV-negative clients? If yes, what are they and why?
- 2. Would you consider using this test on all of your HIV-negative clients or just a subset? If just a subset, which ones and why? [Probe: If you think the test would be best for only a subset, how would you minimize stigmatization of that subset of clients?]
- 3. For the HIV-negative clients whom you would use this test on, how frequently would you test them and why?
- 4. If you received test results for an HIV-negative client that showed less than perfect PrEP adherence, how would you use the results to support your clinical decision making? Would you do anything differently than what you are currently doing for poor adherence? Why?

2827 2828 2829

2830

2831

2832

2833

2834

Feasibility and Acceptability of PrEP Adherence Testing

- 5. Do you believe implementing this type of test would be feasible in your clinic or in another setting? Why or why not?
- 6. Do you think providers need training to deliver these test results? Why/why not?
- 7. How do you think this test could be implemented? That is, who would do the test? Where would the test be done? Who would give the results? When would the results be given?

2835 2836

2837

2838

IV. Conclusion

8. We have reached the end of our interview. Do you have any other concerns or thoughts about this test that we have not yet discussed? Is there anything that we didn't ask that we should have asked?

2839 2840 2841

[Interviewer]: Thank you again for participating in our study!

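### The provider interview guide (Appendix V) has no question on the experience of delivering the feedback messages, on what helped or hindered it, or on confidence, although Section 6.2 promises these topics for a primary outcome

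*Combined protocol and SAP*

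**What the plan says.** Section 6.1 lists as its second primary outcome the "feasibility to provide feedback on the POC urine tenofovir assay to participants for healthcare providers".

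Section 6.2 (Feasibility for research healthcare providers) plans up to 8 key informant interviews at study end. The interviewees are the nurses, doctors and counselors "who delivered the counseling messages to intervention arm participants after receiving the results of the POC urine TFV assay". The interviews are meant to cover acceptance, barriers, facilitators and confidence about adherence testing with the assay, within a technology-acceptance model. The section then adds: "These interviews will also elicit barriers and facilitators to delivering the TFV assay-informed counseling messages".

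Appendix V is the guide for these interviews. Its introduction says: "The goal of this interview is to understand your feelings about this test and to discover potential applications and use cases for this test". Part III opens with "Now I'm going to ask you about what you thought about this new test". The items closest to feedback are "If you received test results for an HIV-negative client that showed less than perfect PrEP adherence, how would you use the results", "Do you think providers need training to deliver these test results", and a question on how the test could be implemented, which includes who would give the results and when.

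Section 6.4 (Feasibility) adds counted measures: retention at 12 months, missed visits, and the proportions of planned urine assessments completed and messages delivered in the intervention arm. The proportions get 95% confidence intervals. The provider interviews are to be analyzed with the same qualitative methods as the participant interviews.

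**The concern.** The interviewees are chosen because they gave the messages, and the outcome is about giving feedback. The written questions concentrate instead on the strip and on future use of the test. If the guide is followed as printed, what providers found easy or hard about telling a woman her result would come up only by chance, and so unevenly across a very small sample.

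Section 6.3 says the trial is meant to examine feasibility rather than to reach statistical significance on hair levels, and the Study Summary says its findings will inform a larger trial. What made feedback workable or difficult is therefore a main product of this pilot. The interviews take place once, and no analysis can supply answers to questions that were not put.

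**Working it through.** No statistical calculation applies. The check sets each question of Appendix V beside what Sections 6.1 and 6.2 promise.

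**Step 1. Topics promised.** (a) Feasibility of giving feedback (6.1). (b) Barriers and facilitators to delivering the assay-informed messages (6.2). (c) Acceptance of, barriers to, facilitators of and confidence about testing with the assay (6.2).

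**Step 2. Questions in Appendix V.** The numbered questions total 6 + 2 + 4 + 3 + 1 = 16.

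| Block | Questions | Content | Delivery of messages in the trial? |
|---|---|---|---|
| Opening | 1-6 | Role, time in role, current adherence monitoring, clients' adherence, women's comfort in reporting problems, existing clinic support | No; routine care |
| Part III, clarity | 1-2 | First thoughts, likes and dislikes, whether results were clear | No; the test |
| Applications | 1-3 | Benefits and harms, whom to test, how often | No |
| Applications | 4 | How the provider would use a poor-adherence result | Hypothetical use only |
| Feasibility and acceptability | 5 | Whether implementing the test would be feasible | Test in general |
| Feasibility and acceptability | 6 | Whether providers need training to deliver results | Results, in general terms |
| Feasibility and acceptability | 7 | Who would test, where, who would give results, when | Results, prospective |
| Conclusion | 8 | Other concerns, anything not asked | Open, undirected |

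**Step 3. Result.**
- Experience of giving the positive or negative message (Figure 8): 0 of 16.
- Barriers or facilitators to delivering the messages: 0 of 16.
- Confidence, whether in testing or in giving messages: 0 of 16.
- Delivering or giving results, in general or prospective terms: 2 of 16 (questions 6 and 7).
- Hypothetical use of a result: 1 of 16 (Applications, question 4).

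Result-based counseling does appear in part II, but as something the interviewer tells the provider, not as a question.

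**Step 4. Fit with the providers' role.** Part II of the guide has the provider dip the strip and obtain the result from it. Sections 3.3, 5.5 (Point of care urine monitoring test) and 5.10 give performing and interpreting the test to laboratory staff, who pass a yes or no to the research provider; the provider then counsels. The SOP in Appendix VI also has the provider apply the urine, so the appendices and the body text differ on this. On the body text, the guide dwells on a step these providers did not carry out and has no question on the one they did.

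**Step 5. Whether Section 6.4 fills the gap.** The proportion of messages delivered shows how often delivery happened. It carries no information on why a message was easy, hard or missed, which is what topic (b) promises.

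**The case against.** The best case for the guide as it stands has five parts.

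1. **Delivery is touched on.** Questions 6 and 7 concern training to deliver results and who would give them and when. They are put to people who have just done it, and the training item asks why. A reader might infer that the guide never asks about feedback at all. These items do not support that reading. They remain general, concern results rather than messages, and do not ask what helped or hindered.
2. **The focus on the assay is deliberate.** Section 6.2 sets out to study perceptions of the assay, applies a technology-acceptance model, and looks ahead to providers running the test themselves. Message delivery is one added sentence. This explains the forward-looking items, and those should stay. It does not remove the commitment in that sentence or the definition in Section 6.1.
3. **Confidence is promised only for testing.** That is correct: Section 6.2 does not promise a measure of confidence in giving a message, nor of added visit time. But the guide has no confidence item of either kind.
4. **The interviews are semi-structured.** There is a closing catch-all question, and coding leaves room for new themes. An interviewer may raise message delivery, but no written probe directs it, so coverage would depend on the interviewer.
5. **Feasibility has other evidence.** The Section 6.4 counts stand, and the documents set no feasible-or-not rule that this gap would corrupt.

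A reader might also take the Study Summary's mention of "structured surveys and qualitative interviews" as a promise of a structured survey of providers. That sentence covers participant acceptability and provider feasibility together, and Section 6.2 specifies a survey only for participants. The documents do not clearly promise one for providers.

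**Conclusion.** The concern holds in limited form. Appendix V has no item on providers' trial experience of delivering the messages, on what helped or hindered delivery, or on confidence. Section 6.2 says the interviews will elicit the barriers and facilitators and aims to understand confidence about testing. The size is 0 of 16 numbered questions, in a set of at most 8 interviews that are the only source of providers' own views on a primary outcome.

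It does not follow that the feasibility outcome is unsupported, since Section 6.4 counts messages delivered and questions 6 and 7 bear on giving results. Nor would the number of planned feedback visits measure the gap: it says how often messages were due, not what the interviews would miss.

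The conclusion assumes that Appendix V is the guide actually used and that interviewers keep broadly to it. The change is worth making because it is cheap and the omission cannot be repaired after the interviews.

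**What to change.** Add a short open block to part III of Appendix V, asked about the trial itself:

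1. How did giving the positive message go, and how did giving the negative message go?
2. What helped or hindered giving them? Probes: wait for the laboratory result, privacy, the counseling guide, a client disputing the result, visit time.
3. How confident did you feel using the assay result with clients?

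Reword question 4 under Applications from a hypothetical to what the provider did on receiving such a result in the trial. Section 3.4 says no clinical decisions will be based on the result, so the reworded item should ask about its use in counseling. Correct the part II description so that it matches who performed and read the test, and reconcile it with Appendix VI.

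Analyze the answers with the qualitative methods already in Section 6.4; no new scale or table is needed. The cost is an amendment of the guide with the usual ethics approval, and a few extra minutes in each of up to 8 interviews that the guide already puts at 30-60 minutes. No extra staff, visits or samples are required. The amendment should be in place before the first provider interview.
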